5.4 Randomisation

After eligibility has been confirmed, patients will be randomised to the trial. Randomisation will be performed centrally by Imperial Cancer Clinical Trials Section (CCTS) using the study database. There will be no option for manual randomisation. Upon randomisation each patient will be allocated a unique subject ID which should be used in all future correspondence. Please refer to the eCRF Completion Manual for further details on patient randomisation.

RESOLVE	C/43/2022	Imperial College London	v2.0 10 th July 2023
---------	-----------	-------------------------	------------------------------------

In this open-label study, randomisation will be on a 1:1 basis between second evacuation and pembrolizumab prior to second evacuation arms. Randomisation will be stratified according to baseline hCG since this has been shown to strongly influence the probability of cure following second evacuation. Based on historical data, we have carried out simulations to show that randomising patients within pre-defined hCG values corresponding to expected median or quartile limits results in balanced distribution of hCG values between the two arms in over 95% of simulated trials. The Trial Statistician will be responsible for holding the randomisation code securely until the final analysis of the study but also to enable the interim analysis.

After eligibility has been confirmed, an archival tissue sample in the form of formalin fixed paraffin embedded (FFPE) tumour block and/or diagnostic tissue section will be collected from each patient.

5.5 Visit Schedule

Table 2: Schedule of Assessments: Second evacuation only

Procedure	Pre-screening	Baseline/screening Day -3 to 0	Day 7 ¹	2 weeks post evacuation ²	6 weeks post evacuation ²	12 weeks post evacuation ²	Every 2 weeks post evacuation until normalisation of hCG	Every month following normal hCG and until 1 year post evacuation
Informed Consent		X						
Medical History & Demographics		X						
Physical Exam		X		X	X			
Performance Status		X		X	X			
Vital Signs		X						
Haematology	X							
Biochemistry	X							
Coagulation	X							
Viral Screen (Hep B, Hep C, HIV)	X							
Thyroid Function Tests and Cortisol		X						
Tumour marker blood hCG	X						X	
Research Blood Sample		X		X	X	X		
Archival Tissue		X						
Imaging - Chest X-ray	X							
Imaging - Uterine ultrasound scan	X		X					
Randomisation		X						
Surgical evacuation			X					
Urine hCG							X	X
Adverse Events				X	X	X		
Concomitant Medications		X						

RESOLVE	C/43/2022	Imperial College London	v2.0 10 th July 2023
---------	-----------	-------------------------	------------------------------------

1. Visit is permitted to be performed two days prior or after scheduled timepoint.
2. Visit is permitted to be performed three days prior or after scheduled timepoint.

Table 3: Schedule of Assessments: Pembrolizumab arm

Procedure	Pre-screening	Baseline/Screening Day -3 to 0	Day 0	Day +7 ¹	Day +11 ¹	Day +14 ¹	2 weeks post evacuation ²	6 weeks post evacuation ²	12 weeks post evacuation ²	Every 2 weeks post evacuation until normalisation of hCG	Every month following normal hCG and until 1 year post evacuation
Informed Consent		X									
Medical History & Demographics		X									
Physical Exam		X			X		X	X	X		
Performance Status		X			X		X	X	X		
Vital Signs		X			X						
Haematology	X				X			X	X		
Biochemistry	X				X			X	X		
Coagulation	X				X			X	X		
Viral screen (Hep B, Hep C, HIV)	X										
Thyroid Function Tests and Cortisol		X						X	X		
Tumour marker blood hCG	X			X	X					X	
Research Blood sample		X				X	X	X	X		
Archival Tissue		X									
Imaging – Chest X-ray	X										
Imaging – Uterine ultrasound scan	X					X					
Imaging – Optional Magnetic Resonance Imaging			X ³			X ⁴					
Randomisation		X									
Pembrolizumab			X								

RESOLVE	C/43/2022	Imperial College London	v2.0 10 th July 2023
---------	-----------	-------------------------	------------------------------------

Surgical evacuation						X					
Urine hCG										X	X
Adverse Events					X		X	X	X		
Concomitant Medications			X								

1. Visit is permitted to be performed two days prior or after scheduled timepoint.
2. Visit is permitted to be performed three days prior or after scheduled timepoint.
3. Visit is permitted to be performed anytime from randomisation to before Pembro administration.
4. Visit is permitted to be performed within two days prior to the second evacuation

5.6 Study Schedules

Scheduled visits, and their relevant assessments, will be conducted according to the randomised treatment arm – please refer to tables 2 and 3.

5.7 Follow-up

Following second evacuation, patients in both arms will undergo standard of care urine and blood hCG monitoring every 2 weeks until hCG normalisation and then monthly urine hCG measurement for up to 1 year post evacuation. Failure of second evacuation to result in disease control is defined as per national guidelines (rise or plateau in hCG, hCG over 20,000 IU/L at 4 weeks, heavy vaginal bleeding). Patients will additionally have a clinical review and toxicity check at 2, 6 and 12 weeks post evacuation.

5.8 Procedures, Assessments and Laboratory Evaluations

(i) Demographic data

Patient month and year of birth will be collected at screening. For equality and diversity purposes, gender including gender reassignment; sexual orientation; marital status; disability; ethnicity, religion; geographical location and socioeconomic status and smoking status/history) will also be collected with all questions being optional to answer.

(ii) Medical history to include cancer history and treatment

A medical history will be taken. This history will detail the patient's cancer, including details of prior anti-cancer therapies. Any other relevant medical history and treatments will also be recorded. Concurrent diseases, i.e., other medical conditions that are ongoing from the start of the study, will be documented as adverse events if they worsen.

(iii) Vital signs

Vital signs including height (screening only), weight, body temperature, pulse, blood pressure and BMI will be recorded as indicated in the schedule of assessment tables. Vital signs may be assessed at any time during the visit; however, pulse and blood pressure should be measured after at least 10 minutes rest.

(iv) Physical exam

A complete physical examination will be performed as indicated in the schedule of assessment tables. The following examinations should be undertaken: general

appearance; skin; eyes, ears, nose, mouth and throat; head, neck and thyroid; chest; cardiovascular; abdomen; extremities; genitalia; spine; musculoskeletal; lymph nodes; neurological; other. The outcome of the examinations will be assessed to include whether normal, abnormal (clinically significant or not clinically significant) or not done.

(v) ECOG performance status

ECOG performance status will be performed as indicated in the schedule of assessments tables according to criteria as follows:

Table 4: ECOG Performance status

0	Fully active, able to carry on all pre-disease activities without restriction
1	Restricted in physically strenuous activity but ambulatory and able to carry out work of a light or sedentary nature. For example, light housework, office work
2	Ambulatory and capable of all self-care but unable to carry out any work activities. Up and about more than 50% of waking hours
3	Capable of only limited self-care, confined to bed or chair 50% or more of waking hours
4	Completely disabled. Cannot carry on any self-care. Totally confined to bed or chair
5	Death

(vi) Laboratory evaluations:

The following laboratory evaluations will be conducted as indicated in the schedule of assessments tables, with collection and analysis according to standard practice at the relevant site.

- **Haematology:** White blood cell count (WBC) with differential, haemoglobin (Hgb), haematocrit (Hct) and platelet count.
- **Biochemistry:** Chem 7 (sodium [Na], potassium [K], chloride [Cl], bicarbonate [CO₂], creatinine [Cr], glucose), calcium, phosphate, magnesium, urea and electrolytes. Creatinine clearance calculated based on Cockcroft-Gault estimate.
- **Liver function tests (LFTs):** ALT or AST (either or both as per local practice), alkaline phosphatase (ALP), albumin, lactate dehydrogenase (LDH) and total bilirubin.
- **Coagulation screen:** APTT, PT
- **Thyroid function tests (TFTs):** TSH, free T3, free T4.
- **Viral Screen:** Hepatitis B, Hepatitis C and Human Immunodeficiency virus (HIV)
- Human Chorionic Gonadotropin (hCG) blood or urine test

(vii) Tumour assessment

Tumour assessment will be performed by serial hCG measurement. Complete response is defined as normalisation of hCG levels (<5 IU/L) post second evacuation.

(viii) Thoracic x-ray and uterine ultrasound Scan (USS)

A thoracic x-ray and uterine ultrasound scan (USS) will be undertaken as part of pre-screening to ascertain if disease is low or high risk. The USS will be transvaginal, unless adequate imaging to determine eligibility criteria can be obtained by a transabdominal scan.

Additionally, a second uterine USS will be undertaken prior to second evacuation to ensure the disease remains amenable to second evacuation (disease within the uterine cavity and not within 5mm of the serosal surface). The second scan will routinely be carried out as a transvaginal study.

For the Pembrolizumab arm only, two optional MRI scans may be performed (funding permitted); the first of which would be given during the screening period and the second within two days before the second evacuation visit. The MRIs will be used for exploratory analysis separate from the main study.

(ix) Assessment of adverse events

Adverse events will be assessed as indicated in the schedule of assessments table, according to the data detailed in section 7.1.

(x) Assessment of concomitant medications

Concomitant medications will be assessed as indicated in schedule of assessments table, with the following data recorded for each medication:

- Name
- Start date / whether ongoing / end date
- Indication
- Dosage
- Frequency
- Route of administration

If a COVID-19 vaccine is administered during treatment, this will be recorded as a concomitant medication, with each dose recorded separately

(xi) Research samples

An archival tissue sample in the form of formalin fixed paraffin embedded (FFPE) tumour block will be collected from each patient, as well as blood (up to 20 ml) at baseline. Further blood for research and fresh tissue from second evacuation will be collected as indicated in schedule of assessments table. Tissues will be studied in an ongoing research project to better understand the mechanisms of immune evasion and sensitivity in GTN.

Further details on sample processing, handling and shipment are provided in the Laboratory Manual.

(xii) Sample storage and analysis

Written informed consent which include the collection and use of specified biological samples and a full chain of custody will be maintained for all samples throughout the study.

PIs are responsible for maintaining full traceability of biological samples collected from patients while these are in storage at their site, until shipment to Imperial College London ECMC Laboratory and from return to site and/or disposal. Any person(s) responsible for temporarily holding samples, e.g. sub-contracted service provider must keep full traceability of samples from initial receipt of sample to onward shipment, return or disposal as appropriate.

Samples shipped to the ECMC Laboratory will be stored and analysed according to this protocol, a separate study laboratory manual, and any additional documentation produced by CCTS as required.

Imperial College London, CCTS has oversight of each sample's lifecycle through internal procedures and monitoring of study sites.

Archival tissue samples will be retained for further study and will be registered with the Imperial College Healthcare NHS Tissue Bank (ICHTB). Samples will be returned once the planned translational project is complete or earlier upon written request.

5.9 Incidental Findings

Incidental findings are defined as observations of potential clinical significance unexpectedly discovered in research participants and unrelated to the purpose of the study. These may include for example abnormal or unexpected findings from laboratory samples or from radiology images.

We would not expect many incidental findings to be identified during this study. However, any incidental findings that were discovered would be reported back by the Chief Investigator and study team to the treating oncologist and participant.

RESOLVE	C/43/2022	Imperial College London	v2.0 10 th July 2023
---------	-----------	-------------------------	------------------------------------

If an incidental finding is observed during the study, and it is considered a significant abnormality, then the study team should report these to the PI who should take action accordingly. It is the PI's responsibility to ensure findings are communicated to the participant, GPs or other clinicians as appropriate. Incidental findings should be reported to the sponsor trials team.

RESOLVE	C/43/2022	Imperial College London	v2.0 10 th July 2023
---------	-----------	-------------------------	------------------------------------

6. TREATMENTS

6.1 Investigational Medicinal Product Details

Pembrolizumab is an IMP for the purposes of this study. It is currently approved by NHS England for treatment of patients with GTN who have failed chemotherapy.

The Summary of Product Characteristics (SmPC) will be used as reference safety information (RSI) for the study, as submitted for CTA and amended where required during the trial e.g., when submitting DSURs, substantial amendment to study etc.

6.2 Labelling and Packaging

Packaging and labelling of pembrolizumab should be according to local practice. There are no trial-specific requirements.

6.3 Storage and Dispensing

Storage of pembrolizumab must be in line with the current relevant SmPC.

Once the pembrolizumab has been diluted for infusion, it should ideally be used immediately. If not used immediately it should be refrigerated at 2-8°C for a maximum of 96 hours (including up to 6 hours at $\leq 25^{\circ}\text{C}$) and not frozen. If refrigerated, the vials and/or IV bags must be allowed to come to room temperature prior to use.

Dispensing will be according to local standard practice.

6.4 Dosage, Duration and Compliance

A single 200 mg IV dose of pembrolizumab will be administered in the treatment arm.

6.5 Accountability

The investigator and appropriately trained and delegated staff will document the receipt, dispensing, administration and destruction of pembrolizumab as per local policy.

Please refer to the IMP Handling Manual for further details.

6.6 Drug interactions / Precautions / Contraindications

Interactions

No formal pharmacokinetic drug interaction studies have been conducted with pembrolizumab. Since pembrolizumab is cleared from the circulation through catabolism, no metabolic drug-drug interactions are expected.

RESOLVE	C/43/2022	Imperial College London	v2.0 10 th July 2023
---------	-----------	-------------------------	------------------------------------

Systemic corticosteroids or other immunosuppressants can be used after starting pembrolizumab to treat immune-related adverse reactions.

Precautions

None. Management of specific adverse events is detailed in section 6.9.

Contraindications

Hypersensitivity to the active substance or to any of the excipients: L-histidine, L-histidine hydrochloride monohydrate, sucrose, polysorbate 80, water for injections.

6.7 Overdose of IMP

There is no information on overdose with pembrolizumab.

In case of overdose, patients must be closely monitored for signs or symptoms of adverse reactions, and appropriate symptomatic treatment instituted.

6.8 Dose Modifications for Toxicity

The pembrolizumab dose given will be a single dose before second evacuation. Any toxicity resulting from the Pembrolizumab should be treated as per standard of care.

6.9 Study drug administration

Drug administration is as per local standard procedures.

6.10 Pre-medications / Non-IMP details

There are no premedications.

6.11 Withdrawal from Study

Withdrawal from the study refers to discontinuation of study treatment and study procedures and can occur for the following reasons:

- Participant decision
- In the intervention arm, development of indications for urgent chemotherapy in the period between receiving pembrolizumab and awaiting second evacuation, discussed further below*

**Patients who develop vaginal bleeding, rising hCG >100,000 IU/L or any other indication for urgent chemotherapy will be withdrawn from the study to commence chemotherapy as determined by the treating team.*

(i) Procedures for Withdrawal from Study

In the event of a patient withdrawing from the study, no further visits or follow up will be conducted. The primary reason must be recorded in the eCRF and the patient's medical records. Any data and samples already collected will be retained and analysed.

Where the patient has withdrawn due to an AE, the investigator should follow the procedures in section 7.0.

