	
Pembrolizumab will be given as a single 200 mg IV dose with second evacuation 14 days later. In the SOC arm, patients will undergo second evacuation on day 10 post randomisation.
 
Between pembrolizumab administration and second evacuation, patients will have 2 clinical reviews to determine whether any new indication for urgent chemotherapy has arisen and commence this immediately if so.
 
Cancer tissue for research will be collected at the point of second evacuation and patients will subsequently enter a standard of care surveillance protocol.

PRIMARY ENDPOINT	Feasibility of the approach, defined as the proportion of eligible patients who consent to randomisation and the proportion of patients randomised to the intervention arm who complete protocol treatments.
SECONDARY ENDPOINTS	
Proportion of patients who achieve a sustained complete response following second evacuation and no further anti-cancer therapy, defined as normalisation of hCG and no rise by 1 year post procedure.
 
Incidence of adverse effects of second evacuation and pembrolizumab within 30 days and 12 weeks respectively, assessed by Common Terminology Criteria for Adverse Events (CTCAE v5.0, 27 Nov 2017).

ESTIMATED RECRUITMENT PERIOD	12 months
END OF TRIAL DEFINITION	The end of the trial is defined as collection of the last data point for the last patient
IMP	
Name: Pembrolizumab
 
Formulation: Concentrate for solution for infusion
 
Dose: Single 200 mg single dose in the intervention arm.
 
Route of administration: Intravenous (IV)

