2.2 Secondary Objective and Endpoint

Objectives	Endpoints
To assess the rate of surgical cure with and without pembrolizumab.	Proportion of patients who achieve a sustained complete response following second evacuation and no further anti-cancer therapy, defined as normalisation of hCG and no rise by 1 year post procedure.
To assess the safety of a single dose of pembrolizumab prior to second evacuation versus second evacuation alone.	Incidence of adverse effects of second evacuation and pembrolizumab within 30 days and 12 weeks respectively, assessed by Common Terminology Criteria for Adverse Events (CTCAE v5.0, 27 Nov 2017).

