7.4 Reporting Procedures

All adverse events should be reported. Depending on the nature of the event the reporting procedures below should be followed. Any questions concerning adverse event reporting should be directed to the study coordination centre in the first instance. A flowchart is given below to aid in the reporting procedures.

(i) 7.4.1 Non serious AR/AEs

All such toxicities, whether expected or not, should be recorded in the toxicity section of the relevant case report form and sent to the study coordination centre within one month of the form being due.

(ii) 7.3.2 Serious AR/AEs

Fatal or life threatening SAEs and SUSARs should be reported on the day that the local site is aware of the event. The SAE form asks for nature of event, date of onset, severity, corrective therapies given, outcome and causality (i.e. unrelated, unlikely, possible, probably, definitely). The responsible investigator should sign the causality of the event. Additional information should be sent within 5 days if the reaction has not resolved at the time of reporting.

SAEs

An SAE form should be completed and emailed to the study coordination centre for all SAEs within 24 hours. However, relapse and death due to disease under study and hospitalisations for elective treatment of a pre-existing condition do not need reporting as SAEs.

SUSARs

In the case of suspected unexpected serious adverse reactions, the staff at the site should:

Complete the SAE case report form & send it immediately (within 24 hours,), signed and dated to the study coordination centre together with relevant treatment forms and anonymised copies of all relevant investigations.

[figure not shown]
Or

Contact the study coordination centre by phone and then send the completed SAE form to the study coordination centre within the following 24 hours as above.

The study coordination centre will notify the MHRA, REC and the Sponsor of all SUSARs occurring during the study according to the following timelines; fatal and life-threatening within 7 days of notification and non-life threatening within 15 days. All investigators will be informed of all SUSARs occurring throughout the study.

Local investigators should report any SUSARs and /or SAEs as required by their Local Research Ethics Committee and/or Research & Development Office

Safety Reporting Overview

* Unless identified in the protocol as not requiring immediate reporting

Contact Details for Reporting SAEs and SUSARs:

[contact]

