8.3.4 Safety Analysis

Safety data analysis will be conducted on all subjects randomised within the trial. Data will be collected on the number of patients who are withdrawn from the study in order to commence chemotherapy due to tumour progression. The number and proportion of patients who experience complications arising from second evacuation will be reported. In the intervention arm, the number and percentage of subjects experiencing an AE and the number of events will be reported. Information regarding severity will be examined with a focus on Grade 3-5 events using the Common Terminology Criteria for Adverse Events (CTCAE v5.0).

RESOLVE	C/43/2022	Imperial College London	v2.0 10 th July 2023
---------	-----------	-------------------------	------------------------------------

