9.11 Informed Consent

Consent to enter the study must be sought from each participant only after a full explanation has been given, an information leaflet offered and time allowed for consideration. Signed participant consent should be obtained. The right of the participant to refuse to participate without giving reasons must be respected. After the participant has entered the trial, the clinician remains free to give alternative treatment to that specified in the protocol at any stage if he/she feels it is in the participant's best interest, but the reasons for doing so should be recorded. In these cases, the participants remain within the study for the purposes of follow-up and data analysis. All participants are free to withdraw at any time from the protocol treatment without giving reasons and without prejudicing further treatment.

RESOLVE	C/43/2022	Imperial College London	v2.0 10 th July 2023
---------	-----------	-------------------------	------------------------------------

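### Section 6.11 ends scheduled safety follow-up for dosed patients moved to chemotherapy before evacuation, in conflict with section 9.11

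*Protocol*

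**What the plan says.** Section 6.11 treats withdrawal as one act that stops both study treatment and study procedures. It lists two reasons: the participant's own decision, in either arm, and, in the intervention arm, an urgent need for chemotherapy arising after pembrolizumab and before evacuation. Patients in the second group are to be withdrawn. For any withdrawal, "In the event of a patient withdrawing from the study, no further visits or follow up will be conducted". What exists at that point is kept: "Any data and samples already collected will be retained and analysed". If the cause was an adverse event, the investigator is sent to section 7.

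Section 9.11 covers the clinician who departs from protocol treatment in the patient's interest: "In these cases, the participants remain within the study for the purposes of follow-up and data analysis".

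The chemotherapy route is planned for. The Trial Summary says that between dose and evacuation "patients will have 2 clinical reviews to determine whether any new indication for urgent chemotherapy has arisen".

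On safety, section 2.2 defines the endpoint as "Incidence of adverse effects of second evacuation and pembrolizumab within 30 days and 12 weeks respectively". Section 8.3.4 adds: "Safety data analysis will be conducted on all subjects randomised within the trial". Section 5.7 sets the checks: "Patients will additionally have a clinical review and toxicity check at 2, 6 and 12 weeks post evacuation". Section 7.4 opens with a general duty: "All adverse events should be reported".

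On efficacy, section 2.2 defines a proportion: hCG normalised, no rise by one year, no further anti-cancer therapy. Section 8.3.3 instead names a recurrence free survival rate at a one-year landmark counted from evacuation.

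**The concern.** A patient switched to chemotherapy by the treating team fits both sections. Section 6.11 ends her follow-up; section 9.11 continues it. A site cannot do both.

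If the site follows 6.11, the loss falls on patients who have received the investigational drug, during the period in which its adverse effects are to be counted. The 8.3.4 adverse-event percentages for the intervention arm would then combine patients followed on a schedule with patients who had at most one scheduled check after the dose. An analysis plan can describe that imbalance but cannot recover visits that were never held.

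A second difficulty remains even if 9.11 governs. The later safety visits are dated from evacuation, so a dosed patient who is never evacuated has no date from which to count them.

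**Working it through.** The protocol states no figure on this point, so there is none to reproduce. The check is a reading of the two rules and of the visit schedule, followed by simple day counts.

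**1. The two rules.** Section 6.11 makes withdrawal for urgent chemotherapy mandatory and leaves the chemotherapy to the treating team. Section 9.11 applies when a clinician gives treatment other than that in the protocol. The same patient satisfies both conditions, and the outcomes are opposite. No other passage ranks one above the other.

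**2. What Table 3 schedules.** Inputs: dose on Day 0 (Table 3); evacuation 14 days later, 2 days either side (section 1.4.2), so Days 12 to 16; Day +11 visit with 2 days either side, so Days 9 to 13; post-evacuation visits with 3 days either side (Table 3 footnotes).

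- 2 weeks post evacuation: 12 + 14 − 3 = Day 23 to 16 + 14 + 3 = Day 33
- 6 weeks: 12 + 42 − 3 = Day 51 to 16 + 42 + 3 = Day 61
- 12 weeks: 12 + 84 − 3 = Day 93 to 16 + 84 + 3 = Day 103

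Adverse-event checks after the dose are at Day +11 and at these three visits. Thyroid and cortisol tests after the dose are at the 6- and 12-week visits only.

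| Intervention-arm patient | Scheduled adverse-event checks after dose | Thyroid/cortisol tests after dose |
|---|---|---|
| Evacuated, completes schedule | 4 | 2 |
| Withdrawn after Day +11 check | 1 | 0 |
| Withdrawn before Day +11 check | 0 | 0 |

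**3. Share of the 12-week window without planned follow-up.** Section 2.2 does not say when the 12 weeks start, so both readings are shown.

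*From the dose.* The window is 12 × 7 = 84 days. This route lies between dose and evacuation, so withdrawal falls on some day w no later than 16. The uncovered share is (84 − w)/84:

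- w = 7: 77/84 = 92%
- w = 11: 73/84 = 87%
- w = 14: 70/84 = 83%
- w = 16: 68/84 = 81%, the smallest possible

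*From evacuation.* There is no evacuation date, so the window never opens.

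The measure is days followed by no planned contact, not visit dates inside the window. A check can record events since the previous visit, so for an evacuated patient the 12-week post-evacuation visit, although after Day 84, can still pick up events that began before it.

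**4. How many patients.** The protocol does not say. Section 8.1.1 expects 90% of 10 intervention patients to complete, with a floor of 70%. If patients are independent, the chance of at least one non-completer is 1 − 0.9^10 = 65%, or 1 − 0.7^10 = 97% at the floor. These count every reason for not completing, so they are upper figures for the chemotherapy route. One patient is 1/10, or 10 percentage points, of an adverse-event percentage in that arm.

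**The case against.** The best defence is that 6.11 is a specific rule and 9.11 general consent text about discretionary departures, so the specific rule governs. That is a fair reading, but the protocol does not state it, and adopting it confirms the loss of scheduled follow-up.

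A second defence is that safety data are not abandoned. Data already collected are kept, withdrawals due to an adverse event go to section 7 (bleeding, a named trigger, may itself be one), and 7.4 exempts no withdrawn patient from reporting. Sections 8.3.2 and 8.3.4 also report these withdrawals, so the unequal follow-up would be visible. All this stands, and it limits the point to scheduled ascertainment: section 7 sets no visits or blood tests after withdrawal.

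Third, the 81% depends on counting from the dose, while a check at 12 weeks post evacuation suggests counting from evacuation. That is right, and the figure is conditional. The other reading leaves these patients with no window at all.

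Two stronger inferences are tempting and unsupported:

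- *Follow-up can stop early only in the intervention arm.* The chemotherapy route is specific to that arm, but participant-decision withdrawal carries the same sentence and applies to both.
- *The cure comparison is damaged.* A patient given chemotherapy already fails the 2.2 definition, so her status is known without further hCG data. Section 8.3.1 names ITT as the primary analysis population, and no passage removes unevacuated patients from the denominator. Section 8.3.3 may be loose shorthand for the 2.2 proportion.

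**Conclusion.** The conflict between 6.11 and 9.11 is real and unresolved. Following 6.11 ends scheduled safety follow-up in dosed patients whom 2.2 and 8.3.4 require to be assessed. For each such patient, at least 68 of 84 days (81%) have no planned follow-up if the 12 weeks run from the dose, and both post-dose thyroid/cortisol tests are lost; if the weeks run from evacuation, the window has no start. The number of affected patients is unknown. Unscheduled adverse-event reporting continues, and the two feasibility endpoints are unaffected. The point should be fixed because data not collected cannot be recovered later.

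The difference between 8.3.3 and 2.2 is a minor mismatch of wording and adds no weight to this conclusion.

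**What to change.** - In 6.11, separate stopping protocol treatment from withdrawing consent to data collection, in line with 9.11.
- Unless consent is withdrawn, continue adverse-event collection to 12 weeks by contact or at routine visits, and record routine results that are already available.
- State the pembrolizumab dose as the time origin for dosed patients who are not evacuated.
- Minor: word 8.3.3 as the 2.2 sustained-response proportion over all randomised patients, counting those given further anti-cancer therapy as not achieving it.

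The cost is amendment wording plus a few contacts and eCRF entries for each affected patient. Sample size, treatment, the feasibility endpoints and the clinical rules on withdrawal and chemotherapy stay as they are.
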